3.3 Study Duration, Enrollment and Number of Participants

Enrollment will continue until 38 participants have been enrolled in each group (76 participants total). The medical ICU (MICU) admits approximately 150 per month, 40-50% of whom require mechanical ventilation. Based on a previous evaluation of lung protective ventilation in our hospital, approximately 45% of our patients requiring mechanical ventilation have a BMI ≥ 40 . Therefore, the MICU conservatively admits approximately 24 patients a month that meet inclusion criteria. Based on expected enrollment of at least 3-4 participants per month, the trial is expected to complete enrollment within 24 months. Each patient's participation will last 28 days or until death or hospital discharge.

3.4 Study Population

Inclusion Criteria: Obese adults (BMI ≥ 40) admitted to the MICU at UNC Hospital or the ICU at Vidant Medical Center ECU with acute respiratory failure requiring mechanical ventilation.

Exclusion Criteria:

1. Refusal to give consent by the subject or their LAR
2. Abdominal compartment syndrome
3. Chest tube for pneumothorax
4. Having been on a ventilator for >4 days
5. Suspicion of or known intracranial hypertension
6. Anticipated extubation within 24 hours
7. Chronic ventilator dependence
8. Condition that precludes placement of an esophageal balloon (esophageal or nasopharyngeal pathology preventing insertion of the esophageal balloon catheter, severe thrombocytopenia or coagulopathy)
9. Incarceration
10. Not expected to survive >48 hours
11. Unable to obtain consent from subject or LAR
12. Unable to obtain consent due to a language barrier

4 STUDY PROCEDURES

4.1 Screening/Enrollment

Daily screening of all intubated patients in the MICU at UNC Hospital and the ICU at Vidant Medical Center ECU will be conducted by the research team. Intubated patients will be evaluated for inclusion and exclusion criteria. For patients meeting inclusion criteria, the primary clinical team will then be approached for permission to enroll prior to approaching families of patients for enrollment.

4.2 Randomization, Concealment, and Blinding

Patients will be randomized 1:1 in random blocks of 2, 4, or 6 to optimal PEEP vs standard PEEP management. Allocation concealment will be performed through the REDCap randomization module. Due to the obvious treatment differences between the two groups, blinding of treatment group will be impossible. However, we will have one outcome assessor who will have access only to the data necessary to determine the primary outcome (VFD at 28-days), and this assessor will be blinded to treatment group using built-in REDCap tools.

4.3 Intervention procedures

All patients in both groups will have an esophageal balloon catheter inserted by a research investigator. The catheter will be inserted into their nare while upright (head of bed >30 degrees) to a depth slightly more than the estimated distance from the lower sternum to the back of the ear (typically around 60 cm). Gastric positioning will be confirmed with abdominal compression testing and the catheter then retracted 10 – 20cm into the lower esophagus. Placement will be confirmed with the presence of cardiac oscillations on the esophageal probe. The probe will then be secured to the patient's nasal opening using tape.

Pressures (Pes, Paw, and Ptp) are measured directly through the ventilator. Values of Paw, Pes, and Ptp will be collected daily in both groups.

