Study Design	Randomized-controlled clinical trial. Patients will be enrolled within 4 days of mechanical ventilation and randomized 1:1 to titration of PEEP based on esophageal balloon pressures or based on the "High PEEP" ARDSnet PEEP/FiO ₂ table. All patients will have esophageal balloons placed with baseline measurement of Ptp. Patients randomized to the intervention arm will then undergo titration of PEEP based on Ptp measurements to achieve "Optimal PEEP," defined as end expiratory Ptp of 0 to +2 cm H ₂ O.

Subject Population key criteria for Inclusion and Exclusion:	
Inclusion Criteria: Obese adults (BMI ≥ 40) admitted to the medical ICU at UNC Hospitals or Vidant Medical Center at ECU with acute respiratory failure requiring mechanical ventilation.
 
Exclusion Criteria:
 
 1. Refusal to give consent by subject or LAR 2. Abdominal compartment syndrome 3. Chest tube for pneumothorax 4. Having been on a ventilator for >4 days 5. Suspicion of or known intracranial hypertension 6. Anticipated extubation within 24 hours 7. Chronic ventilator dependence 8. Condition that precludes placement of an esophageal balloon (esophageal or nasopharyngeal pathology preventing insertion of the esophageal balloon catheter, severe thrombocytopenia, or coagulopathy) 9. Incarceration 10. Not expected to survive >48 hours 11. Unable to obtain consent from subject or LAR 12. Unable to obtain consent due to a language barrier
Number Of Subjects	76 patients
Study Duration	Each subject's participation will last for up to 28 days. The entire study is expected to last about 12-24 months.
Study Phases	
(1) Screening: Screening for eligibility and obtaining consent for enrollment.
 
(2) Pre-Intervention: Esophageal balloon placed and baseline data collected.
 
(3) Intervention: PEEP titrated to achieve Optimal PEEP in the intervention group. Ptp Measurements will be obtained daily and adjustments to PEEP will occur daily.
 
(4) Subject Completion/Withdrawal: Study will conclude for each patient at 28 days after enrollment or hospital discharge.

Efficacy Evaluations	Primary evaluation measurements that will be used to assess the efficacy of the intervention are ventilator free days at day 28. Differences between control and intervention groups will be attributed to differences in PEEP management.

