6.2 Statistical Methods

All continuous variables (see 5.2) will be described using mean and standard deviation, with associated 95% confidence intervals, or median with interquartile range as appropriate based on normality of distribution. All categorical variables will be described with frequency and percentage.

To determine if the optimal PEEP has an effect on the duration of mechanical ventilation compared to usual PEEP, the primary outcome will be analyzed with a 2-sided independent t-test. As secondary analysis, the associations between the primary outcome and exposures and demographic variables will be further analyzed using linear regression models.

The impact of optimal PEEP vs standardized PEEP titration will be assessed on all other variables with independent t-tests or chi-square tests as appropriate. All secondary outcomes, as described in 5.2, will be further analyzed with either linear regression models or logistic models, using demographic and exposure variables as predictors.

All tests will be 2-sided, and p-values < 0.05 will be considered significant. Tests with p-values above 0.05 will be considered inconclusive. Missing values will be ignored.

No interim analyses for efficacy or futility are planned, but interim analyses will be conducted for safety.

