6.3 Sample Size and Power

We utilized preliminary data from earlier studies of mechanical ventilation in the obese to establish a baseline. With a mean duration of mechanical ventilation of 7 days with a standard deviation of 2.9 days, we expect the control group to have 21 ventilator free days. We estimate that we could reasonably see an effect in the intervention group that reduces the duration of mechanical ventilation by 3 days. With a power of 80% and alpha=0.05, we would need 16 patients per group, for a total of 32 patients. Would the effect be only a reduction of mechanical ventilation by 2 days, we would need 34 patients in each group for a total of 68 patients. Because the population in our study would be expected to have a lower mean duration of mechanical

ventilation, we anticipate we may find a smaller effect size. Including a possible 10% dropout, we will target a sample size of 76 (38 per group) to safely achieve our goals.

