7.2 Data and Safety Monitoring Plan

All participants will be continuously monitored by critical care nurses under the guidance of critical care physicians per individual ICU protocols.

Stopping rules and procedures

Subject stopping rules will be the development of any of the following after randomization:

- New pneumothorax
 - Pneumothorax is a known risk factor for all patients requiring mechanical ventilation with a case rate of <1% of all mechanically ventilated patients. In previous studies of optimal PEEP determination using esophageal balloon-guided pressure measurement, no pneumothoraces were observed. We believe the study procedures will be safe for both arms, and that the intervention arm will be at lower risk for this outcome. However, development of a pneumothorax will necessitate a chest tube and will invalidate the measurement of pleural pressure. Therefore the study procedures must be stopped.
- Epistaxis requiring intervention
 - In the event of epistaxis requiring packing or intervention, the esophageal balloon will be removed and the study subject's participation in the study will end.
- Hypotension
 - In the event a patient experiences a drop in mean arterial pressure (MAP) below 65 mm Hg or a significant change in vasoactive medication requirement (>10 mcg/min dose of norepinephrine equivalent), that is felt by the clinical ICU team to possibly be related to the intervention, the study subject's PEEP will be dropped by 2 cm H₂O every 5 minutes until the parameter returns to an acceptable range (as determined by the clinical ICU team) or until the PEEP reaches the pre-intervention level. The patient will remain on no higher than this new PEEP for the remainder of the study.

Adverse Event Reporting

All Adverse Events will be documented and graded using CTCAE grading, defined as any patient who develops one of the following (by CTCAE grading):

- grade 3-5 hypotension
- grade 2-5 pneumothorax
- grade 2-5 epistaxis

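### The protocol does not say whether randomization comes before or after balloon placement and baseline Ptp; if it comes first, avoidable losses fall after allocation

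*Combined protocol and SAP*

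**What the plan says.** Section 4.2 states: "Patients will be randomized 1:1 in random blocks of 2, 4, or 6 to optimal PEEP vs standard PEEP management". It gives no time point relative to the balloon. Section 4.3 then states: "All patients in both groups will have an esophageal balloon catheter inserted by a research investigator". Position is confirmed there by abdominal compression testing and cardiac oscillations.

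In the synopsis, the Study Design row mentions 1:1 randomization, then balloons and baseline Ptp for all patients, then: "Patients randomized to the intervention arm will then undergo titration of PEEP based on Ptp measurements". The Study Phases row puts the balloon and baseline data in a Pre-Intervention phase, after screening and consent and before titration. Randomization is listed in none of the phases.

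Exclusion 8 in 3.4 covers a "Condition that precludes placement of an esophageal balloon" and lists obstructing pathology, severe thrombocytopenia and coagulopathy. No section says what happens when an attempted placement fails or cannot be confirmed.

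Section 7.2 opens its rules with: "Subject stopping rules will be the development of any of the following after randomization". One of these is epistaxis requiring intervention, after which the balloon is removed and participation ends. Section 4.4 also makes nasopharyngeal bleeding a ground for early completion. Section 6.2 ignores missing values and defines no analysis population. The synopsis model adjusts for Ptp without saying that this is the baseline value.

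**The concern.** Exclusion 8 screens out predictable problems, but only the insertion itself shows whether a balloon can be placed and read. If the arm is already assigned, a failure at that step becomes a post-randomization event.

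Its consequences differ by arm even when the failure rate does not. In the intervention arm, Ptp sets both the daily PEEP and the PEEP used in the spontaneous breathing trial (5.1), so that part of the strategy cannot be delivered. In the control arm PEEP comes from a table, and care hardly changes. Keeping such patients dilutes the contrast. Dropping them may remove different kinds of patients from each arm, and in an open-label trial of 76 a few such losses matter. Section 3.3 enrolls to 38 per group without saying whether a failed placement counts or is replaced.

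There is a lesser point. A research investigator who knows the arm would position the catheter from which baseline Ptp is read, and might try harder with a doubtful catheter in one arm than in the other.

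**Working it through.** **Order of events, text against text.**

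| Place | What it implies |
|---|---|
| Synopsis, Study Design | Randomization, then balloon and baseline Ptp, then titration: suggests allocation first |
| 4.2 followed by 4.3 | Randomization, then insertion in both groups: suggests allocation first |
| Synopsis, Study Phases | Balloon before titration, randomization not placed: fits either order |
| 7.2, stopping rules | Counts events after randomization: does not date the insertion |

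Allocation first is the more natural reading, but it is an inference.

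**The plan's own sample size.** Inputs from 6.3 and 6.2: SD 2.9 days, difference 2 days, two-sided alpha 0.05, power 80%, dropout 10%. The standardized difference is 2 / 2.9 = 0.690. The exact two-sample t-test needs 33.99, so 34 per arm, as stated. For a 3-day difference it needs 15.69, so 16, as stated. Dropout: 34 / 0.9 = 37.8, so 38 per arm and 76 in total. The plan's figures reproduce.

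**Room for placement losses.** 76 x 0.9 = 68.4 evaluable against 68 needed. General dropout at the assumed 10% uses the whole allowance.

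**Extra loss at placement.** The documents give no rate, so the fractions f below are assumptions. Evaluable patients per arm = 38 x 0.9 x (1 - f). Power is from the exact t-test at a standardized difference of 0.690. The total needed to keep 34 evaluable per arm is 2 x 34 / (0.9 x (1 - f)), with each arm rounded up.

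| f (assumed) | Evaluable per arm | Power | Total N to keep 34 per arm |
|---|---|---|---|
| 0 | 34.2 | 80.3% | 76 |
| 2% | 33.5 | 79.4% | 78 |
| 5% | 32.5 | 78.1% | 80 |
| 10% | 30.8 | 75.9% | 84 |
| 15% | 29.1 | 73.4% | 90 |

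The table treats every placement loss as a missing primary outcome and as additional to the 10%. If the 10% already includes such losses, power stays at about 80%. If placement is confirmed before allocation, these failures never enter the 76 and f is zero.

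**The case against.** A reader might infer that the protocol has fixed allocation before placement. The documents do not support that. Section order is weak evidence, because allocation (3.2) is also described before eligibility (3.4) and screening (4.1). The one explicit phase sequence would allow randomization at the end of Pre-Intervention. The wording in 7.2 limits which events count, and since the catheter stays in for daily readings, bleeding can also come later.

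A failed placement is also not automatically a lost outcome. No rule withdraws a patient because the catheter could not be passed, and ventilator-free days come from the EMR (5.2). Exclusion 8 already removes the obvious predictors of failure and bleeding. The intervention is not wholly undeliverable either, since the speaking-valve requirement after tracheostomy needs no balloon.

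A reader might further infer that knowledge of the arm contaminates the primary analysis through baseline Ptp. It does not: 6.2 makes an unadjusted t-test primary and regression secondary, Ptp is not labelled baseline, and the ventilator reads the value.

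All of this stands, and it limits the size of the point. It does not remove it. The order is still unstated, a failed attempt still has no rule, and nothing requires outcome collection once participation ends.

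**Conclusion.** The point holds as an unspecified sequence with a real risk under its more natural reading; it does not hold as a proven sequencing error. The power cost is modest: about 80% down to about 78% to 76% for an assumed extra 5% to 10% loss, and only if those patients have no primary outcome. The more important harm is selective loss of randomized patients, which the documents give no figures to quantify. It rests on three features of the text: participation ends after epistaxis needing intervention, missing values are ignored, and no analysis population is defined. The covariate issue is secondary. Because both arms receive the balloon, nothing in the design requires allocation first, so this is a cheap improvement worth making.

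**What to change.** - In 3.2, 4.2, 4.3 and the synopsis phases, state that REDCap releases the allocation only after consent, confirmed balloon placement and entry of baseline Pes, Paw and Ptp.
- Count a patient without confirmed placement as not randomized and outside the 76, and report how many there were.
- Name the synopsis covariate as baseline Ptp.
- Align 7.2 and the denominators in 7.3. The 7.2 rules run from randomization and the DSMB triggers count enrolled subjects, so insertion events before randomization must be captured explicitly as safety events.
- State that patients lost after randomization, including those with later bleeding, are followed for ventilator-free days to day 28 and analyzed as allocated. Reordering does not cure these later losses.

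If the sponsor keeps allocation first, the last item becomes essential, and placement failures should be reported by arm.

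The cost is protocol wording and one REDCap gate on fields already collected; the target stays at 76. There are two downsides. A few consented patients will have a balloon attempt without being randomized, although either arm would have involved that attempt. Inference is also limited to patients in whom a balloon can be placed, and the report should say so.

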4.4 Participant Completion/ Withdrawal

Participants will complete the study at the time of death or the conclusion of 28 days, whichever occurs first.

Early completion of the trial for each participant will occur if any of the following outcomes are met:

- a. Patient or family withdraw consent for the study
- b. The clinical team feels that the patient no longer meets appropriateness for the study
- c. Patient develops an adverse effect felt possibly related to the intervention (refractory hypotension, nasopharyngeal bleeding, pneumothorax, etc)

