Safety Evaluations	Periodic review will be performed by the NC TraCS DSMB. They will review aggregate safety data after 25, 50, and 75% enrollment to ensure there are not safety differences between the groups in hypotension requiring vasopressors and development of pneumothorax. All patients will have

continuous monitoring of HR, BP, and oxygenation per ICU protocol to monitor patient safety.

Statistical And Analytic Plan

This is a randomized, controlled trial to evaluate the effect of using Optimal PEEP based on an esophageal balloon measurement on duration of mechanical ventilation. We hypothesize that using Ptp to identify optimal PEEP will reduce time on the ventilator and therefore increase the ventilator free days at day 28. The primary outcome is the number of ventilator-free days, defined as the number of days alive and ventilator-free by day 28. Differences between the two groups in the primary outcome will be analyzed using independent t-tests and a linear regression model adjusting for BMI, abdominal girth, and Ptp.

DATA AND SAFETY MONITORING PLAN

The PI will be responsible for maintaining patient data and ensuring accuracy of the data collected. All patient data will be collected using REDCap through the NC TraCS system. REDCap allows for immediate data validation and range setting to reduce the likelihood of erroneous data entry. Data created for analysis will be de-identified and secured on a password protected UNC School of Medicine network hard drive. All investigators will be trained on completing the electronic case report form.

Patient safety will be monitored with continuous cardiovascular monitoring by the critical care team. Subject stopping rules will be in place to end the study intervention, including refractory hypotension, development of pneumothorax, or changes in oxygenation or hemodynamics that the primary team feels may be related to changes in PEEP.

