3 INVESTIGATIONAL PLAN

3.1 Study Design

We will conduct an open label randomized controlled clinical trial to evaluate the impact of titration to Optimal PEEP compared to use of a standardized PEEP table on the duration of mechanical ventilation in obese patients with acute respiratory failure. Patients will be followed for 28 days to evaluate for ventilator-free days. Blinding of the clinical team will not be possible due to the differences in treatment approach, including the performance of spontaneous breathing trials.

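### The exit rules can end a randomised patient's participation before day 28 without securing the primary outcome, and the plan neither requires analysis as randomised nor states one consistent rule

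*Combined protocol and SAP*

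**What the plan says.** **Text that ends participation.** Section 4.4 defines completion as death or day 28, then adds: "Early completion of the trial for each participant will occur if any of the following outcomes are met". Trigger (a) is withdrawal of consent. Trigger (b) is "The clinical team feels that the patient no longer meets appropriateness for the study". Trigger (c) is "Patient develops an adverse effect felt possibly related to the intervention (refractory hypotension, nasopharyngeal bleeding, pneumothorax, etc"). Under Stopping rules in 7.2, after epistaxis needing packing or intervention the balloon comes out and the subject's "participation in the study will end". The synopsis (Study Phases, item 4) and section 3.3 also close a patient's participation at hospital discharge, which 4.4 does not list.

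**Text that ends only the intervention.** The synopsis (Data and Safety Monitoring Plan) says "Subject stopping rules will be in place to end the study intervention, including refractory hypotension, development of pneumothorax". That sentence goes on to include changes in oxygenation or haemodynamics that the primary team attributes to PEEP. For pneumothorax, 7.2 says "Therefore the study procedures must be stopped". For hypotension, 7.2 lowers PEEP and keeps the patient in: "The patient will remain on no higher than this new PEEP for the remainder of the study".

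**Outcome and analysis.** Section 3.1 says "Patients will be followed for 28 days to evaluate for ventilator-free days", and table 5.2 takes VFD from the electronic medical record (EMR) at completion. Section 6.1 places the assessment after the subject has completed the study. Section 6.2 specifies a two-sided t-test and leaves missing values out. No section defines an analysis population or says that patients are analysed in their assigned arm.

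**The concern.** Three rules act together. A patient can be closed out early, the outcome is tied to completion and not explicitly to day 28, and a missing outcome drops out of the test. No single rule excludes anyone, but followed literally the three together can.

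The trial is open label. Trigger (b) is a judgement by staff who know the arm. Trigger (c) depends on whether an event is thought related to the intervention. Such exits may depend on both arm and severity, so losing their outcomes can bias the comparison as well as cost power. The blinded assessor described in 4.2 does not help with patients whose outcome is never assessed.

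The hospital-discharge clause raises the same question for a different group. The plan does not say how the days between discharge and day 28 are ascertained.

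**Working it through.** **1. The plan's own figures.** Section 6.3 uses SD 2.9 days, a 2-day effect, two-sided alpha 0.05 and 80% power. The t-test solution is 33.99, so 34 per group, as stated. Allowing for 10% dropout, 34/0.9 = 37.8, so 38 per group and 76 in total, as stated. The plan therefore budgets for 76 − 68 = 8 losses. The sample size is not in question.

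**2. What each section does with a stopped patient.**

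| Event | Ends participation | Ends or limits the intervention only |
|---|---|---|
| Clinical team judges patient no longer appropriate | 4.4(b) | Synopsis, where the reason is a PEEP-related change |
| Pneumothorax | 4.4(c) | Synopsis; 7.2 (procedures stop) |
| Hypotension | 4.4(c), if refractory | Synopsis, if refractory; 7.2 (capped PEEP, stays in) |
| Epistaxis | 4.4(c), if possibly related; 7.2, if it needs intervention | None |
| Hospital discharge | Synopsis; 3.3 | Not listed in 4.4 |

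The same event can lead to different handling depending on which section a site follows.

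**3. Size of the shift if exiters are dropped.** Let x of 38 patients leave an arm, with true VFD on average d below the full-arm mean m. The mean of those who stay is

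[38m − x(m − d)]/(38 − x) = m + d·x/(38 − x).

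With a exits in one arm and c in the other, the between-arm difference shifts by

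d·[a/(38 − a) − c/(38 − c)],

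in favour of the arm with a exits when this is positive. The documents give neither exit counts nor d. I assume d = 3 to 5 days, the same in both arms.

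| Exits (a/c) | Bracket | d = 3 | d = 5 |
|---|---|---|---|
| 1/0 | 1/37 = 0.0270 | 0.08 | 0.14 |
| 2/0 | 2/36 = 0.0556 | 0.17 | 0.28 |
| 5/3 | 5/33 − 3/35 = 0.0658 | 0.20 | 0.33 |
| 6/2 | 6/32 − 2/36 = 0.1319 | 0.40 | 0.66 |
| 4/4 | 0 | 0 | 0 |

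Against the 2-day planning effect, one or two exits in one arm amount to 4% to 14% (0.08/2 to 0.28/2), and the 6/2 split at d = 5 to 33% (0.66/2). The shift is proportional to d. The discharge clause is not sized, because nothing in the documents allows it.

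**4. Direction.** If a is the intervention arm, the shift favours the intervention; if a is the control arm, it favours control. Trigger (c) is worded around the intervention, which points to the first. But 7.2 expects the intervention arm to be at lower risk of pneumothorax, the control arm's High PEEP table reaches 24 cm H₂O (Appendix 12.1), and trigger (b) applies to both arms. The documents do not settle the direction.

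**5. If VFD is collected for everyone.** The shift from dropped patients is zero by construction. With all 38 per group, power for 2 days is 84.3%, against 80.0% at 34 per group (t-test, SD 2.9), before any dilution from stopped patients.

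**The case against.** The best defence is that nothing in the plan says data collection stops or that stopped patients are excluded. Leaving out missing values matters only if VFD is missing. VFD comes from the EMR, 3.1 promises 28 days of follow-up, and 4.2 provides an assessor for VFD at 28 days. Section 6.3 itself derives 21 control-group VFD as 28 − 7, which counts days through to day 28. The synopsis treats even clinician-judged, PEEP-related changes as ending the intervention only. A reasonable reader could conclude that early completers still receive a day-28 VFD from the chart.

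Much of this stands. It shows that collection is feasible and probably intended, so the stronger reading, that the plan has chosen to exclude stopped patients, is not supported. But these are general statements, while 4.4 and the epistaxis rule are specific and say that participation ends. None of the general statements covers a patient who has been closed out.

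The defence is also right on size. The safety information cited is reassuring: no adverse effects in a small balloon-guided trial (7.1), and pneumothorax below 1% of ventilated patients (7.2). Both arms have the balloon, so epistaxis should be roughly balanced and may have little to do with prognosis. The 8 budgeted losses must also cover consent withdrawal, so a 6/2 split made up wholly of prognostic exits is an unfavourable case.

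**Conclusion.** The point stands as a conflict between sections with a possible bias, not as a demonstrated one. Sections 4.4(b), 4.4(c), the 7.2 epistaxis rule and the discharge clause can end participation before day 28. Nothing then guarantees that VFD is collected or that the patient is analysed as assigned.

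On the assumed 3 to 5 day deficit, one or two exits in one arm only shift the difference by about 0.08 to 0.28 days. Larger imbalances reach about 0.66 days, and balanced exits with equal deficits give nothing. Exit counts, split and deficit are all assumptions.

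Two further inferences should be resisted. One is that the bias favours the intervention; it could go either way. The other is that the false-positive rate is roughly trebled. A rate of 15.2% does follow from a 6/2 split at d = 5, but only if all 8 losses are prognostic exits and the SD is 2.9. That SD describes ventilation duration, not VFD. At an assumed SD of 6, the same split gives 7.3%.

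The change should be made because it is cheap and removes the ambiguity, not because a large distortion has been shown.

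**What to change.** - **4.4 and 7.2:** state that any stop other than withdrawal of consent to follow-up ends or caps the PEEP strategy only, and that the patient remains in the trial for outcome purposes. This covers triggers (b) and (c) and the epistaxis rule, and brings them into line with the synopsis and the pneumothorax and hypotension rules.
- **Synopsis (Study Phases) and 3.3:** state that hospital discharge does not end VFD ascertainment before day 28.
- **Collection:** take VFD from the EMR to day 28 for every randomised patient whose consent to follow-up stands.
- **6.2:** state that the primary t-test includes all randomised patients in their assigned arm on this basis, and report stops by arm and reason.

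The cost is a wording amendment and some extra record review. That review is harder for patients discharged before day 28, whose later course may not be in the hospital's EMR. Keeping stopped patients in will dilute the estimated effect somewhat, as expected when patients are analysed as assigned. The sample size stays at 76.
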